At all planned visits and phone contacts (except for visits to apply a CGM sensor) the Investigator or designee will review glucose results (especially looking for hypoglycemia), adverse events, changes in concomitant medications, and changes in IP or bolus insulin use, and the following procedures will be performed: vital signs, body weight, urinalysis, urine pregnancy testing for women of childbearing potential, and an FBG test.

[figure not shown]
Additional procedures at study visits are as follows: at Weeks 8, 16 and 26, blood for HbA1c will be collected; during the visits at Weeks 12 and 26, subjects will wear their CGM sensors to the site for the site staff to safely remove it, and they will bring their Mealtime & Insulin Dose Record for the site staff to review, and blood will be collected for routine hematology and chemistry testing, TSH and free T4 and TSH; at Weeks 12 and 26, blood will be collected for AIA; and at Week 26, a 12-lead ECG and physical examination will be performed.

A subset of additionally consented subjects will have blood drawn at Day 1 and Weeks 2, 4, 8, 12, 16, 20, and 26 for optional PK (insulin glargine, M1, and M2 concentrations).

If a subject discontinues the study prematurely, site personnel will make a reasonable effort to perform all study activities scheduled for Visit 9 (end of treatment [EOT] visit).

Additionally, it is very important for site personnel to encourage subjects to visit the site at Week 26 ( $\pm$  4 weeks) (and Week 12  $\pm$  1 week if applicable) for a blood sample to be obtained for AIA and HbA1c measurements.

Figure 1 and Table 1 show the study design and study-related procedures, respectively.

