#### **8.5.12 Assignment to Treatment**

Randomization will be performed through IXRS. The Investigator or designee will access the IXRS to randomize enrolled subjects. The IXRS system will assign a unique randomization number and study medication kit number. Randomization will be stratified by country. No subject may be randomized more than once, and no randomization number will be assigned to more than 1 subject.

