The 90% CI will be estimated using a pattern mixture model that uses multiple imputation (MI) analyzed using Analysis of Covariance (ANCOVA) with treatment and stratification factor of country (CNTRY) included as fixed effects and baseline HbA1c included as a covariate. Separately in each treatment group, the imputation will use outcomes in subjects who discontinued treatment prior to Week 26 but returned to provide a visit Week 26 HbA1c sample to impute outcomes in subjects without actual visit Week 26 recorded results under the MNAR assumption. Limits of the imputed value will use the minimum of HbA1c values and the maximum of all HbA1c values assessed, and rounded to the nearest integer. These values are found in the database to be minimum as 5 and the maximum as 13. No imputation will be performed for missing baseline HbA1c. Equivalence will be assessed based on the 90% CI; no p-values will be computed. Change from baseline in HbA1c between Gan & Lee Insulin Glargine Injection and Lantus® will be considered equivalent if the 90% CI is within the margins (-0.4%, 0.4%).

For EMA submission, non-inferiority in change from baseline in HbA1c between Gan & Lee Insulin Glargine Injection and Lantus® will be tested using the following null hypothesis:

$$H_0: (\mu_1 - \mu_2) \geq 0.4$$

Against the alternative hypothesis of:

$$H_1: (\mu_1 - \mu_2) < 0.4$$

with a 1-sided $\alpha=0.025$.

In addition, the same non-inferiority test with a margin of 0.3% will be performed.

The 95% CI will be estimated using a pattern mixture model that uses MI analyzed using ANCOVA with treatment and stratification factor of country (CNTRY) included as fixed effects and baseline HbA1c included as a covariate. Separately in each treatment group, the imputation will use outcomes in subjects who discontinued treatment prior to Week 26 but returned to provide a visit Week 26 HbA1c sample (labeled as the unscheduled) to impute outcomes in subjects without actual visit Week 26 recorded results under the MNAR assumption. No imputation will be performed for missing baseline HbA1c.

Analysis of HbA1c will follow a hierarchical testing strategy: first, non-inferiority will be tested using a margin of 0.4% and only if this test is significant, then non-inferiority will be tested using a margin of 0.3%.

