- 4) Mixed model repeated measure (MMRM): this sensitivity analysis will include all post-baseline HbA1c measures from each time point as the dependent variable. The independent variables in the model include fixed effects for treatment assignment (2 levels), time (3 post-baseline times), treatment-by-time interaction, country, and covariate terms for the baseline HbA1c score and baseline HbA1c score-by-time interaction (which allows the effect of baseline covariate parameter to change over time). An unstructured covariance matrix will be used to model the inter-dependencies among the repeated measures. However, if the model does not converge, an alternative covariance matrix will be used which is appropriate for the repeated measurements (e.g., first-order autoregressive). Given the missing data, the Kenward-Roger approximation will be used for calculating the denominator degrees of freedom and adjusting standard errors. If a structured variance-covariance matrix is used, sandwich estimator will be used to estimate the variance of the treatment effect estimate. The FAS will be used to generate the results. (Table 5, Analysis 5)

instead examine the results under a MNAR assumption. If the tipping point analysis reveals that the "tipping point" is at an unreasonable shift, then the robustness of the study results under the MAR assumption are supported.

A sample SAS code fragment is provided below for reference (note: actual seeds to be used in the analysis are presented below):

```
proc mi data=<data> nimpute=10 seed= 337850 out=<out_data> minimum=. 0 0;  
  class trt;  
  monotone reg;  
  mnar adjust(week_26 /shift = <shift> adjustobs=(trt='Gan & Lee Insulin Glargine Injection'))  
    adjust(week_26 /shift = -<shift> adjustobs=(trt='Lantus'))  
  var trt base_HbA1c week_26;  
run;
```

The following shift values will be used (increase for Gan & Lee Insulin Glargine Injection and decrease for Lantus® simultaneously): 0, 0.2, 0.4, etc. until the conclusion of equivalence or non-inferiority will change, the equivalence 2-way tipping point analysis utilizes a shift in both directions (additionally decrease for Gan & Lee Insulin Glargine Injection and increase for Lantus®). The ANCOVA analyses will be performed as described in Section 11.7.1.1.

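### The HbA1c tipping-point code imputes Week 26 from treatment and baseline only; adding the Week 8 and Week 16 values would be a cheap improvement

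*SAP*

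**What the plan says.** The tipping-point code in SAP 11.7.1.3 opens with "proc mi data=<data> nimpute=10 seed= 337850", names treatment as its only class variable, uses monotone regression, and lists "var trt base_HbA1c week_26". Week 26 is the variable being imputed, which leaves treatment and baseline HbA1c as the only predictors. The code is introduced with "A sample SAS code fragment is provided below for reference".

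Three other places bear on this:

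- **Schedule.** Protocol 8.1: "at Weeks 8, 16 and 26, blood for HbA1c will be collected". Table 1 and Sections 9.5 and 9.8 agree.
- **Analysis model.** For the fit after imputation, SAP 11.7.1.3 states: "The ANCOVA analyses will be performed as described in Section 11.7.1.1". The ANCOVA given under SAP 11.7.1 has "treatment and stratification factor of country (CNTRY) included as fixed effects and baseline HbA1c included as a covariate". Country is the stratification factor (Protocol 8.5.12: "Randomization will be stratified by country").
- **MMRM.** In the same SAP section, "this sensitivity analysis will include all post-baseline HbA1c measures from each time point as the dependent variable". That model has three post-baseline times and a country term, but no shift.

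The Protocol lists no imputation covariates and leaves the details to the SAP (Sections 12.6.1 and 12.8.1).

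**The concern.** At shift zero, this imputation model assumes that, given treatment arm and baseline HbA1c, whether Week 26 is missing carries no further information about its value. A subject who leaves after Week 16 with a high reading is imputed as though that reading had not been taken.

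Dropout linked to interim control is plausible in this trial. Protocol 8.4.3.1 lists inadequate response as a reason for withdrawal, the study is open-label, and SAP 5.1 reports more early discontinuation than expected. The SAP judges robustness by how large a shift is needed before the conclusion changes. If the zero point is off, that shift is measured from the wrong origin.

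There is also a loss of precision. Imputing from baseline recovers almost nothing for an ANCOVA that already adjusts for baseline, whereas interim HbA1c would recover part of the missing information. Leaving out country makes the imputation and analysis models differ by one term.

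**Working it through.** The documents give no HbA1c standard deviation, visit correlations or missing rate, so there is no plan figure to reproduce. All sizes below rest on assumptions.

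**Inputs from the documents.** 275 subjects per arm (SAP 5.1); margins 0.4 and 0.3 (SAP 11.7.1); shifts 0, 0.2, 0.4 and so on, added in one arm and subtracted in the other (SAP 11.7.1.3).

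**Assumed.** Fraction missing f = 0.10 to 0.20 in each arm. Correlations: baseline with Week 26, 0.5 to 0.7; baseline with Week 16, 0.6 to 0.75; Week 16 with Week 26, 0.8 to 0.85. Every dropout has a Week 16 value.

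**1. Precision.** Let r be the partial correlation of Week 16 and Week 26 given baseline. Relative to complete data, the variance factor for the difference is

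- baseline-only imputation: 1/(1 − f);
- with Week 16 added: 1 + [f/(1 − f)](1 − r²).

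The ratio of the second to the first is 1 − f·r², so the standard error ratio is √(1 − f·r²).

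- f = 0.15, r = 0.70: √(1 − 0.0735) = 0.963, a fall of about 4%.
- f = 0.10, r = 0.69: √(1 − 0.0476) = 0.976, about 2%.
- f = 0.20, r = 0.75: √(1 − 0.1125) = 0.942, about 6%.

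Taking every corner of the assumed correlations, r runs from 0.58 to 0.83. The fall at f = 0.15 is then about 3 to 5%. The extremes are √(1 − 0.10 × 0.58²) = 0.983 and √(1 − 0.20 × 0.83²) = 0.929, that is 2 to 7%.

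**2. Bias.** Suppose dropouts in one arm have Week 16 values 0.5 points above what baseline predicts from that arm's observed subjects, and that this carries to Week 26 with partial slope 0.74 to 0.84. Bias in that arm's mean = slope × 0.5 × f.

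- f = 0.15: 0.8 × 0.5 × 0.15 = 0.06.
- f = 0.20: 0.8 × 0.5 × 0.20 = 0.08.

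This is the bias in the difference only if the other arm has no such excess. An equal excess in both arms cancels.

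**3. Position on the shift grid.** A simultaneous shift of +s and −s moves the difference by 2·s·f. With s = 0.2 and f = 0.20 that is 0.08, the same as the bias in step 2.

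**4. Simulation.** Assumptions: 275 per arm, true difference 0, SD 1.0, 5 countries, 10 imputations, ANCOVA with country, shift 0, 400 runs per scenario, all dropout after Week 16. Dropout depends on the Week 16 change in opposite directions by arm, which is deliberately adverse. Correlations are shown as baseline with Week 26 / Week 16 with Week 26.

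| Correlations | Target missing | Log-odds slope per point | Mean estimate, SAP code | Mean estimate with Weeks 8, 16 and country |
|---|---|---|---|---|
| 0.6 / 0.75 | 10% | 0 | 0.001 | 0.001 |
| 0.6 / 0.75 | 10% | 1 | −0.063 | 0.004 |
| 0.6 / 0.75 | 10% | 2 | −0.106 | −0.006 |
| 0.6 / 0.75 | 20% | 0 | 0.014 | 0.012 |
| 0.6 / 0.75 | 20% | 1 | −0.130 | 0.001 |
| 0.6 / 0.75 | 20% | 2 | −0.196 | −0.003 |
| 0.7 / 0.85 | 10% | 0 | −0.002 | −0.002 |
| 0.7 / 0.85 | 10% | 1 | −0.063 | −0.002 |
| 0.7 / 0.85 | 10% | 2 | −0.096 | 0.004 |
| 0.7 / 0.85 | 20% | 0 | −0.001 | 0.001 |
| 0.7 / 0.85 | 20% | 1 | −0.122 | 0.002 |
| 0.7 / 0.85 | 20% | 2 | −0.192 | 0.001 |

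The 0.014 and 0.012 in the fourth row are simulation noise: the same runs with complete data gave 0.011. With slope 0, the standard error fell from 0.0729 to 0.0709 and from 0.0785 to 0.0742 (lower correlations; 10% and 20% missing), and from 0.0651 to 0.0628 and from 0.0701 to 0.0650 (higher correlations). These are falls of about 3 to 7%, including a small share from country. Adding country alone left the bias unchanged and lowered the standard error by about 0.001.

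**The case against.** The strongest reply is that the scan already covers the problem. The shifts continue until the conclusion changes, and for equivalence they run in both directions. The 0.08 bias corresponds to s = 0.2. A bias of 0.20 at 20% missing corresponds to s = 0.20/(2 × 0.20) = 0.5, between the 0.4 and 0.6 steps. This stands. A reader might infer that worsening control before dropout goes untested, or that the HbA1c conclusion itself is biased. The documents support neither: the scan passes through such cases, and the main analysis uses a different imputation. What remains is that the size of the tipping shift is read from a displaced origin.

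Second, the MMRM already uses a dropout's Week 16 value, with country and an unstructured covariance, under MAR. This stands in part: it covers the zero-shift question, but no shift is built on it.

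Third, the bias figure assumes that an on-treatment excess persists. The estimand follows the treatment policy strategy (Protocol 12.8.1), and a subject who changes insulin after leaving may not keep that excess. This stands as a condition on the figure.

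Fourth, it is tempting to say that the trial holds the interim values of all its dropouts. It does not. Subjects who left before Week 8 have no scheduled interim HbA1c, and those who left before Week 16 have at most one. Some may have only an early termination sample (Protocol 9.11).

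Fifth, the code is labelled a sample, and the text that introduces it is cut off in the copy reviewed. Fuller wording may exist. The label alone is a weak defence: the fragment is stated to carry the seeds that will actually be used, and its lower-limit option has three entries, one for each listed variable.

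**Conclusion.** The point holds as an optional improvement to one sensitivity analysis of the key secondary endpoint. The visible tipping-point code leaves out interim HbA1c that is available for subjects who reached Weeks 8 and 16. It also leaves out country, a mismatch with the ANCOVA that hardly matters numerically.

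The precision gain is about 2 to 6% of the standard error for 10 to 20% missing at the central correlations, and up to about 7% at the extremes. It is a ceiling in that every dropout must have a Week 16 value. Bias is about zero unless dropout depends on interim HbA1c differently by arm and the excess lasts to Week 26 after discontinuation. If both hold, about 0.08 at 20% missing is a reasonable illustration, against margins of 0.4 and 0.3. The deliberately adverse simulations gave 0.06 to 0.20. None of the correlations, missing rates or dropout patterns comes from the documents.

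**What to change.** In the tipping-point code:

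- Use `class trt cntry;` and `var trt cntry base_HbA1c week_8 week_16 week_26;`, pooling very small countries in the imputation model.
- Extend `minimum=` to one entry per variable in the same order, for example `minimum=. . 0 0 0 0`. The present three entries would not match six variables.
- Handle intermittent gaps with a preceding step that makes the pattern monotone, or use FCS. The two-step route is cleaner, because under FCS shifted Week 26 values could feed back into the interim imputations.
- Keep the MNAR shift on Week 26 only, as now.

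If SAP text not visible here already lists these predictors, make the code match it.

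The cost is a few lines of SAS and no new data. The downsides are one extra imputation step and possible pooling of small countries. A change made before the randomization assignments are loaded (SAP 10.1) cannot be steered by results; after that, it can be reported as a supplementary run.

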11.7.2 Secondary Efficacy Endpoints

11.7.2.1 Proportion of Subjects Achieving Glycemic Control

The following secondary efficacy variables will be analyzed using the 90% CI of differences in proportions:

- The number and percentage of subjects who achieve an FBG test result of ≤ 6.0 mmol/L (≤ 108.0 mg/dL) at visit Week 26
- The number and percentage of subjects who achieve a HbA1c of $< 7.0\%$ at visit Week 26.

The difference in proportions will be estimated along with the corresponding 90% CI in the FAS using a logistic regression model. Subjects without values available at week 26 will be considered as having not achieved glycemic control. Samples from subjects who have discontinued study but returned to provide assessment for Week 26 will be included for this analysis.

Additionally, number and percentages of subjects who achieve an FBG test result of ≤ 6.0 mmol/L (≤ 108.0 mg/dL) and number and percentages of subjects who achieve a HbA1c of $< 7.0\%$ will be presented by time point and treatment group.

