4.3 Exploratory Objective

- To investigate the retrospective hypoglycemic rate and time in hypoglycemia and hyperglycemia using continuous glucose monitoring (CGM) data
- To examine the relationship between the plasma concentrations of insulin glargine, M1, and M2, and immunogenic response

5. Study Design

This open-label, randomized, multicenter study is designed to compare the immunogenicity, efficacy, and safety of Gan & Lee Insulin Glargine Injection compared with that of Lantus® in subjects with Type 1 diabetes mellitus to determine equivalence.

Subjects between the ages of 18 and 75 who meet the study inclusion criteria and none of the exclusion criteria as defined in the protocol, will be centrally and randomly assigned in a 1:1 allocation ratio to receive

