5.1 Sample Size and Power

Enrollment was planned for 550 subjects overall (275 subjects per treatment group). The primary analysis for the immunogenicity primary endpoint was to be an equivalence test for the difference in proportion of subjects who develop treatment-induced AIAAs between Gan & Lee insulin Glargine Injection and Lantus® using the 2 Wald one-sided tests (TOST) with $\alpha=0.05$ (Chow and Shao 2002 (1)). After scientific and regulatory review, the method to evaluate immunogenicity equivalence will be the 90% confidence intervals of risk difference from the logistic regression analysis (see Section 3.1). Under this newly adopted approach, no power loss is expected.

This sample size of 275 subjects per treatment group was chosen to achieve over 80% power using the TOST equivalence test for two proportions, a risk difference of zero and equivalence margins dependent on the observed treatment-induced AIA rate per Table 3 below. For example, a total sample size of 550 will provide approximately 85% power for the TOST equivalence test using a treatment-induced AIA rate of 30% and a margin of 12% (Table 3). The treatment-induced AIA is defined as newly confirmed positive AIA development or important (at least a 4-fold) increase in AIA titers, after baseline and up to visit Week 26 (see the definition of Primary Endpoint in Section 6.1 and Section 7.2). No drop outs are considered in the calculation. A larger than expected early discontinuation rate was observed as part of study monitoring activities and therefore protocol amendment 3 approved on 25-Apr-2019 included procedures to encourage subjects to return for assessments even if they had discontinued treatment early.

The appropriate similarity margin, based on the actual observed event rate for the intended reference product, will be used for final analysis after database lock as summarized in Table 3 below. The power calculation in the table was adapted for a sample size of 550 using the treatment-induced AIA rate for the reference product. Linear interpolation will be used for values between AIA rates in the table.

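### The Week 26 glycemic-target models name no covariates, which gives up precision if followed as written, and the rule counting missing values as failures has no imputation-based check.

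*SAP*

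**What the plan says.** For the two glycemic-target endpoints, SAP 11.7.2.1 says: "The difference in proportions will be estimated along with the corresponding 90% CI in the FAS using a logistic regression model". It lists no model terms. On missing data it says: "Subjects without values available at week 26 will be considered as having not achieved glycemic control". The next sentence limits that rule: Week 26 samples from subjects who left the study but came back are used.

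The main HbA1c analysis in SAP 11.7.1 is an ANCOVA with treatment and country "included as fixed effects and baseline HbA1c included as a covariate", run on multiply imputed Week 26 values. The SAP's logistic models for treatment-induced, neutralizing and confirmed positive antibodies (11.6.1.1, 11.6.2.4, 11.6.2.5) are each described as adjusted for country. The repeated-measures model (11.7.1.3) and the negative binomial model for hypoglycemia also list their terms.

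Protocol 12.9.3.1 planned a normal-approximation comparison of proportions for these endpoints and named no covariate. Protocol 12.4 makes country the only stratification factor. The available text gives no margin, success criterion, power or alternative missing-data analysis for either endpoint.

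**The concern.** A logistic model with no listed terms beyond treatment would leave out the factor used to stratify randomization and the variable likely to predict the outcome best. Entry allows any HbA1c up to 11.0% with no lower limit (Protocol 8.4.1), so some subjects may already be below 7.0% at baseline. Basal dose is optimized before randomization so that fewer changes are needed later (Protocol 8.5.8). Baseline HbA1c should therefore carry much of the information on who is below 7.0% at Week 26. Leaving it out would widen the interval without any gain.

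The missing-data rule is a separate matter. A subject whose missing Week 26 HbA1c is imputed below 7.0% in the main analysis counts as a failure here. SAP 5.1 reports more early discontinuation than expected, and the trial is open-label, so both the amount of missing data and its balance between arms matter. The two HbA1c results could differ because of the rule alone, and no planned analysis would show it.

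**Working it through.** **Inputs from the documents.** SAP 5.1: "Enrollment was planned for 550 subjects overall (275 subjects per treatment group"); allocation is 1:1. The interval is a 90% CI, so z = 1.645. The documents give no target rate, missing share, HbA1c SD or baseline-to-Week 26 correlation; values for these below are assumptions.

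**The plan's own figure.** The only power figures are for the antibody endpoint: "approximately 85% power for the TOST equivalence test using a treatment-induced AIA rate of 30% and a margin of 12"%, with "a risk difference of zero and equivalence margins dependent on the observed treatment-induced AIA rate".
- SE = √(2 × 0.30 × 0.70 / 275) = 0.0391
- Power = 2Φ(0.12/0.0391 - 1.645) - 1 = 84.6%

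This reproduces the stated 85% and confirms the variance formula used below. It says nothing about the glycemic-target endpoints, which have no power statement.

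**Effect of adjusting for baseline HbA1c.** Simulated trials had 275 per arm, assumed baseline mean 8.0 and SD 1.0. The unadjusted risk difference was compared with the standardized risk difference from a logistic model containing baseline HbA1c.

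| Assumed correlation | SE reduction, no missing data | SE reduction, 15% missing counted as failure |
|---|---|---|
| 0.5 | about 8% | about 4% |
| 0.7 | about 15% | about 11% |
| 0.8 | about 22% | about 20% |

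A separate run at about 0.7 gave SDs of 0.0359 unadjusted and 0.0298 adjusted: 1 - 0.0298/0.0359 = 17%. A fair summary is roughly 5-20%. At assumed rates of 25% and 35% with nothing missing, the unadjusted half-width is 1.645 × √[(0.25 × 0.75 + 0.35 × 0.65)/275] = 6.4 points. A 5% cut gives 6.4 × 0.95 = 6.1, and a 20% cut gives 6.4 × 0.80 = 5.1. Adjusted and unadjusted estimates had practically the same mean (for example -0.0511 and -0.0512), so standardization changes the precision and leaves the target quantity alone. The effect of adding country was not computed, and neither was anything for FBG.

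**Effect of missing-as-failure on the estimate.** Assume missingness is unrelated to outcome within arm. An arm with true rate p and missing share m then shows p(1 - m).

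| True rates, test vs reference | Missing, test vs reference | True difference | Under the rule |
|---|---|---|---|
| 25% vs 35% | 5% each | -10.0 | -9.5 |
| 25% vs 35% | 15% each | -10.0 | -8.5 |
| 25% vs 35% | 10% vs 20% | -10.0 | 22.5 - 28.0 = -5.5 |
| 25% vs 35% | 20% vs 10% | -10.0 | 20.0 - 31.5 = -11.5 |
| 25% vs 25% | 20% vs 10% | 0 | 20.0 - 22.5 = -2.5 |

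**Effect of missing-as-failure on interval width.** At 25% vs 35% with 15% missing in each arm, the observed-to-be-analyzed rates are 21.25% and 29.75%.
- Under the rule: 1.645 × √[(0.2125 × 0.7875 + 0.2975 × 0.7025)/275] = 6.1 points
- Observed cases only: 1.645 × √[(0.25 × 0.75 + 0.35 × 0.65)/(275 × 0.85)] = 6.9 points

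At 60% vs 70% the two figures are 7.0 and 7.2. The rule does not widen the interval relative to using observed cases in either setting.

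**The case against.** **The text is silent on covariates, and it is incomplete.** Section 11.7.2.1 does not say that the model is unadjusted. Parts of the SAP that might settle it, such as Section 3.1 on the change of method and Section 7.1, are not in the available text. This stands. A reader might infer that the SAP deliberately ignores baseline and country, but the supportable statement is that no covariate is named where most of the SAP's other models name theirs. The terms still need writing down.

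**Counting missing as failure is a transparent rule for a responder endpoint.** It is also softened by the use of returning discontinuers' samples, and SAP 11.7.1 allows HbA1c up to study day 210 to count for Week 26. This stands for HbA1c and is a reason to keep the rule. It helps FBG less, because Protocol 9.11 asks returning subjects only for antibody and HbA1c samples. The early-termination visit does repeat the Visit 9 tests, including FBG, but within 14 days of withdrawal and not at Week 26.

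**The rule favours similarity.** A reader might infer this, but it holds only if missingness is similar in the two arms or higher in the arm with the higher target rate. In the opposite case the rule drives the arms apart, as the -11.5 and -2.5 rows show. The documents give no missing shares by arm, so no direction can be claimed.

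**The stakes are small.** The key secondary HbA1c analysis already has baseline adjustment, multiple imputation and several sensitivity analyses, including a tipping point. This also stands.

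**Conclusion.** The point holds as a specification gap with a modest cost in precision. If the model is fitted with treatment only, the SE for the HbA1c target is larger than it would be with baseline HbA1c in the model; adjusting would cut it by roughly 5-20%. That range rests on assumed correlations of 0.5-0.8, an assumed SD of 1.0 and an assumed baseline mean of 8.0, none of which the documents supply. The same argument applies to FBG in principle, but its size is unknown.

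The missing-as-failure rule is a separate and smaller issue. It scales a true difference by (1 - m) under equal missingness and can distort in either direction otherwise. It is not a source of the precision loss.

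A reader might infer that an equivalence conclusion is at risk. The documents do not support that: these are other secondary endpoints with no visible margin or success criterion. What improves is the precision of the estimates and how readily they can be read beside the main HbA1c result.

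**What to change.** In SAP 11.7.2.1:

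1. List the model terms: treatment, country and the corresponding baseline value (HbA1c or FBG). FBG is drawn at both screening and Day 1 (Protocol Table 1), so make clear which value is its baseline, and say how subjects without a baseline value are handled.
2. State that the standardized risk difference is reported with its 90% CI, and how that interval is obtained from the logistic model.
3. Keep missing-as-failure, with returning subjects' samples included, as the main analysis for both endpoints.
4. Add one sensitivity analysis for HbA1c < 7.0%: dichotomize the Week 26 values in each data set from the main multiple imputation, fit the same model, and combine the results.
5. Report the number and share of missing Week 26 values by arm for each endpoint, so that the effect of the rule can be judged.

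The cost is SAP wording and a few lines of code; no new data are needed. The drawback is that the sensitivity analysis shares the imputation assumptions of the main HbA1c analysis, including its reliance on discontinued subjects who returned. It does not cover FBG, which that imputation does not include.
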